8.2 Exclusion Criteria

Participant cannot meet any of the following criteria and must be excluded from participating in this study.

1. Have a history of suspected, confirmed, treated or have other evidence of active tuberculosis, Symptoms may include recurrent fever, fatigue, night sweats, weight loss, oral ulcers, diarrhea, nausea, vomiting, or bleeding,
2. Have any systemic symptoms* within 72 hours before Tice BCG administration or signs of lymphadenopathy, hepatosplenomegaly, or pulmonary disease by physical examination on day of Tice BCG administration,
**Includes fever, chills, malaise, fatigue, headache, night sweats, weight loss, nausea, vomiting, bleeding, diarrhea, abdominal pain, rhinorrhea, cough, wheezing, or shortness of breath.*
3. Have history of any significant acute or chronic medical conditions* or need for chronic medications that, in the opinion of the investigator, will interfere with immunity or affect safety,
**Includes, but is not limited to, disorders of the liver, kidney, lung, heart, or nervous system, or other metabolic or autoimmune/inflammatory conditions. Have any history of excessive scarring or keloid formation.*
4. Have household contact or occupation involving significant contact with someone who is immunocompromised,
**Includes persons with HIV, AIDS, or active cancer; infants (children < 1 year); pregnant women; or persons who are immunosuppressed for approximately 6 weeks (during the time of active ID lesion drainage).*
5. Have a history of epilepsy (does not include febrile seizures as a child),
6. Have a pacemaker, prosthetic valve, or implantable cardiac devices,
7. Have a history of bleeding disorder,
8. Have a known allergy to any Tice BCG components (glycerin, asparagine, citric acid, potassium phosphate, magnesium sulfate, iron ammonium citrate, and lactose),
9. Received blood products or immunoglobulin within 6 months prior to Tice BCG administration,
10. Received immunotherapy within one year prior to Tice BCG administration,
11. Received or plan to receive live attenuated vaccines 4 weeks before or after Tice BCG administration,
12. Received or plan to receive inactivated or killed vaccines 2 weeks before or after Tice BCG administration,

13. Plans to enroll in another clinical trial* that could interfere with safety assessment of the investigational product at any time during the study period,
**Includes trials that have a study intervention such as a drug, biologic, or device.*

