10.6 Evaluations

10.6.1 *Physical Examination and Clinical Assessments*

A physical examination will be performed within 42 days prior to getting BCG and at the final study visit. Participants medical history, concomitant medications, their vital signs (oral temperature, pulse, blood pressure), and height and weight (to calculate Body Mass Index (BMI)) will be collected. Participants will be assessed for lymphadenopathy if indicated based on review of interim medical history and clinical assessment. A medically licensed research team member will review the participants health status and eligibility at the clinic visits.

10.6.2 *Participant Self-monitoring AEs/SAEs and Health Status Records*

Participants will be asked to record their solicited local and systemic reactions, any unsolicited AEs/SAEs (pain, tenderness and drainage) and concomitant medications throughout the study.

They can optionally record their oral temperature as well. They will be sent a redcap survey to record this information. They will be instructed on how to measure and record AEs/SAEs.

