 - Unsolicited AEs/SAEs recorded Days 1-114,
 - Concomitant medications recorded Days 1-114.
- Collection of used dressing/gauze.

Days 4 (clinic visit 6), 5 (clinic visit 7), 6 (clinic visit 8), 8 ± 1 (clinic visit 9), 15 ± 1 (clinic visit 10), and 28 ± 1 (clinic visit 11)

- INH dosing days 4, 5, and 6 only: For the 5 participants assigned to Group 1, they will take INH: oral tablets of either three 100mg tablets (total 300mg) or one 300mg tablet for 3 days post BCG dosing,
- Days 8 ± 1 (clinic visit 9) and 15 ± 1 (clinic visit 10) only: Repeat skin biopsy,
- Assess ID challenge site,
- Review health status and AEs/SAEs that were recorded on the memory aid eCRF device,
- Review concomitant medications,
- Assess for lymphadenopathy if indicated based on review of interim medical history and clinical assessment,

- Targeted physical exam and clinical assessment may be performed if indicated based on review of interim medical history, reactogenicity (as applicable),
- Blood draws via venipuncture for immunogenicity and mycobacteria assays:
 - Day 4: 6.5mls (1.5 tsp),
 - Day 8±1: 74.5mls (5 tablespoons (tbs)),
 - Day 15±1: 56.5mls (4 tbs),
 - Day 28±1: 94.5mls (6 tbs),
- Collect used dressing/gauze,
- Photograph of ID challenge site.

Days 16-114±1

- On-going participant self-evaluations that will be recorded on their memory aid eCRF device for pain, tenderness and drainage. Participants can record their temperature if taken.

Days 56±2 (clinic visit 12) and 84±3 (clinic visit 13)

- Day 56±2 (clinic visit 12) only: Repeat skin biopsy
- Assess ID challenge site (if an abnormal BCG injection site is identified see Abnormal BCG Injection Site Procedures in section 11.3),
- Review health status and AEs/SAEs that were recorded on the memory aid eCRF device,
- Review concomitant medications,
- Assessments for lymphadenopathy if indicated based on review of interim medical history and clinical assessment,
- Targeted general exam and clinical assessment may be performed if indicated based on review of interim medical history, reactogenicity (as applicable),
- Blood draws via venipuncture for immunogenicity and mycobacteria assays:
 - Day 56±2: 94.5mls (6 tbs)
 - Day 84±3: 94.5mls (6 tbs)
- Collect used dressing/gauze,
- Photograph of ID challenge site.

Day 98±1 (clinic visit 14)

- Assess ID challenge site,
- Review health status and AEs/SAEs that were recorded on the memory aid eCRF device,
- Review concomitant medications,

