15.0 ASSESSMENT OF SAFETY

15.1 Specification of Safety Parameters

Safety will be assessed by the frequency and severity of:

1. Tice® BCG-related serious adverse events occurring throughout the course of the study,
2. Solicited Adverse Events – reactogenicity events following Tice® BCG administration:
 - a) Local reactions including pain, tenderness, erythema/redness, and induration/swelling at the injection site.
 - b) Systemic reactions including fever, chills, malaise/fatigue, headache, night sweats, nausea, vomiting, diarrhea, rhinorrhea, cough, and wheezing or shortness of breath.
3. Lesion characterized as erythematous macule, non-erythematous papule, erythematous papule, vesicle, pustule, ulcer, eschar/crust, healed, scar, or keloid,
4. Lymphadenopathy,
5. Clinical safety laboratory adverse events to include WBC, hemoglobin, and platelet count, creatinine and ALT (SGPT),
6. Unsolicited Adverse Events.
 - a) Non-serious adverse events occurring in the 56 days following Tice® BCG administration.

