15.2.3 Additional Adverse Event Characterization and Severity Grading

Lesions at the ID challenge site will be characterized by the study site staff as follows:

1. Erythematous Macule: flat red spot.
2. Non-Erythematous Papule: a small, circumscribed, non-erythematous, palpable elevation in the skin.
3. Erythematous Papule: a small, circumscribed, erythematous, palpable elevation in the skin.
4. Vesicle: clear fluid filled papule.
5. Pustule: cloudy, purulent fluid filled papule.
6. Ulcer: an open lesion on the surface of the skin caused by superficial loss of tissue, often attended by the formation of pus.
7. Eschar/Crust: a lesion with an erythematous base and a central scab (a coagulation product of blood, serum, pus, or a combination of two or more of these).
8. Healed: previously observed lesion that has dried up without any persistent induration, ulcer, or eschar. Redness under an area of previous eschar formation seen after the eschar

has fallen off during the healing process would not be considered active erythema, but instead would be considered evidence of a healed lesion.

9. Scar: replacement of normal skin with fibrous tissue (other than keloid formation).
10. Keloid: nodular scar.

Severity Grading for Lymphadenopathy

The site principal investigator or appropriate sub-investigator licensed to make medical diagnoses will assess the severity of axillary, cervical, and epitrochlear lymphadenopathy bilaterally by applying the grading scale in the following table:

Table 5: Severity Grading for Lymphadenopathy

Grade	Definition
Grade 0 (none)	No palpable nodes, or all nodes < 1 cm (pea-sized), mobile, and nontender.
Grade 1 (mild)	At least one node \geq 1 cm (pea-sized) but < 2.5 cm (cherry-sized), but mobile and non-tender or tender only with firm pressure.
Grade 2 (moderate)	At least one node \geq 2.5 cm (cherry-sized) or tender to light touch or spontaneously reported as painful, but not causing significant limitation of normal everyday activities.
Grade 3 (severe)	At least one node that is tender to light touch or spontaneously reported as painful AND causing significant limitation of normal everyday activities. Any one of palpable fluctuance or heat, fixation to underlying tissues, or visible erythema.

Severity Grading for Clinical Safety Laboratory Adverse Events

Table 6: Severity Grading for Clinical Safety Laboratory Adverse Events - Hematology

Hematology	Mild (Grade 1)	Moderate (Grade 2)	Severe (Grade 3)

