Appendix B: Participant Procedures Table

Clinic Visit	1 (Screening Visit)	2	3	4	5	6	7	8	9	10	11	12	13	14	15	16	17
Day	-42 to -1	0	1	2	3	4	5	6	8±1	15±1	28±1	56±2	84±3	98±1	100±1	112±1	114±1
Week		0							1	2	4	8	12	14		16	
Agents		BCG			INH	INH	INH										
Informed consent	X																
Medical history	X																
Height, weight: BMI	X																
Vitals (pulse, blood pressure)	X																
Urine collection	X																
Pregnancy test (blood)	X																
Pregnancy test (urine)	24 hr before to BCG dose																
General exam and Clinical assessment	X				X*			X*	X*	X*	X*	X*	X*				X
Lymphadenopathy assessment					X*			X*	X*	X*	X*	X*	X*				
BCG injection site evaluation		X	X	X	X	X	X	X	X	X	X	X	X				
Abnormal BCG injection site																	See section 11.3 for procedures
Abnormal BCG injection site clinic visits																	Clinic visits 2x/week from Day 28 ±1 until resolved
Abnormal BCG injection site photos																	Once/week from Days 28 ±1 until resolved
Health status and AE/SAE review		X	X	X	X	X	X	X	X	X	X	X	X	X	X	X	X
Concomitant med review	X					X	X	X	X	X	X	X	X	X	X	X	X
Oral temperature reporting	X																Days 1 - 112 (recorded on Memory Aid eCRF device)
AE/SAE reporting																	Days 1 - 114 (recorded on Memory Aid eCRF device)
Concomitant medication reporting																	Days 1 - 114 (recorded on Memory Aid eCRF device)
ID site pain, tenderness, drainage reporting																	Days 1 - 114 (recorded on Memory Aid eCRF device)
Blood draw	X	X	X	X	X	X			X	X	X	X	X	X		X	X
Skin biopsy					O/S				X/S	O/S		X/S					
Photographs of ID site						X			X	X	X	X	X				X
PPD skin test															X	X	X
Dressing/guaze collection			X	X	X	X			X	X	X	X	X				

* Only if applicable due to medical history and clinical assessment

O = microbiology

X = immunology

S = swab

* Only if applicable due to medical history and clinical assessment

O = microbiology

X = immunology

S = swab

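### Lymphadenopathy is a graded safety parameter and a dosing-day exclusion, but the schedule lists no Day 0 examination and no Table 5 baseline, and every post-BCG node assessment is conditional, so its frequency may be under-reported

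*Combined protocol and SAP*

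**What the plan says.** All references are to the combined protocol and SAP.

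- **Eligibility.** Exclusion 2 (section 8.2) bars anyone with "signs of lymphadenopathy, hepatosplenomegaly, or pulmonary disease by physical examination on day of Tice BCG administration".
- **Scheduled examinations.** Section 10.6.1 states: "A physical examination will be performed within 42 days prior to getting BCG and at the final study visit". The Day 0 list in 11.2 covers BCG, observation of the site, the blood draw, diary training and dressing advice. It lists no physical or node examination.
- **Safety outcome.** Section 15.1 opens with "Safety will be assessed by the frequency and severity of", and its fourth item is "4. Lymphadenopathy". Table 5 in 15.2.3 grades axillary, cervical and epitrochlear nodes on both sides from 0 to 3. Section 5.8.1 names tender nodes near the vaccination site as an occasional BCG reaction.
- **Follow-up of nodes.** The general rule in 10.6.1 is "Participants will be assessed for lymphadenopathy if indicated based on review of interim medical history and clinical assessment". The list in 11.2 for Days 4 to 28 says "Assess for lymphadenopathy if indicated based on review of interim medical history and clinical assessment", and the same condition applies on Days 56 and 84 and at the extra visits for an abnormal site (11.3). In Appendix B every entry in the lymphadenopathy row carries an asterisk, explained as "Only if applicable due to medical history and clinical assessment".

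**The concern.** Two problems meet here.

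The first is a conflict in the text. Eligibility turns on an examination on the day of dosing, while the sections from which staff would work do not list one. A site that followed the schedule alone could give BCG without making the check that exclusion 2 presupposes.

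The second is a measurement problem. A frequency needs a numerator and a denominator that are both observed. Under the conditional rule, Table 5 is completed only for participants whose history or clinical assessment leads someone to palpate. The others have no grade, and nothing says whether they count as Grade 0. Selecting on symptoms or discretion pushes the reported frequency down. Safety and tolerability is a primary objective, and this is a reaction that the protocol itself expects. With 5 participants per group, one missed case moves a group's observed rate by 20 percentage points (1/5).

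**Working it through.** **1. Schedule, set side by side.**

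| Time | Node or physical examination listed | Conditional? |
|---|---|---|
| Screening, Day -42 to -1 | General examination; nodes not named | No |
| Day 0 | None in 11.2; no entry at visit 2 in Appendix B | n/a |
| Days 1 to 3 | Challenge site only in 11.2 | n/a |
| Days 4 to 28, 56, 84 | Nodes, if indicated | Yes |
| Extra visits for an abnormal site (11.3) | Nodes, if indicated | Yes |
| Days 98, 100, 112 | No node assessment | n/a |
| Day 114 | General examination; nodes not named | No |

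Unconditional node examinations listed from Day 0 to Day 112: 0. Unconditional general examinations in the whole study: 2. Column positions in Appendix B may have shifted when the text was extracted, but the gap at visit 2 agrees with the Day 0 list in 11.2. The lymphadenopathy row also has no entry at visit 1 or visit 17.

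**2. Does the trigger fit the scale?** Grade 0 means no palpable nodes, or only small, mobile, non-tender ones, so it cannot be assigned without palpation. Grade 1 is a node of at least 1 cm but under 2.5 cm that is "mobile and non-tender or tender only with firm pressure". Grade 2 is met by a node of 2.5 cm or more even without tenderness. None of these need produce a complaint. Node pain or swelling is not among the solicited reactions in 15.1, and the diary prompts in 11.2 and Appendix B concern pain, tenderness and drainage at the site. History alone therefore need not prompt an examination.

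**3. Does Day 114 recover the information?** Not reliably. The general examination there does not name nodes. Section 15.3 documents non-serious events only to Day 56±2, so a node first found at Day 114 would fall outside that window. Section 15.2.1 says instead that all events on study are documented, and these two passages also conflict.

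**4. The plan's own figures.** Section 18.1 tabulates the chance of at least one event among 5, which is 1 - (1 - p)^5.

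- p = 0.25: 1 - 0.75^5 = 0.763 (stated 0.76)
- p = 0.20: 1 - 0.80^5 = 0.672 (stated 0.67)
- p = 0.15: 1 - 0.85^5 = 0.556 (stated 0.56)
- p = 0.10: 1 - 0.90^5 = 0.410 (stated 0.41)
- p = 0.05: 1 - 0.95^5 = 0.226 (stated 0.23)

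The table reproduces. It treats every event as found, and 18.1 adds that all participants are expected to provide safety data.

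**5. Effect of incomplete ascertainment (illustration).** Let s be the share of affected participants whose nodes are found. The documents give neither s nor a true rate p, so both are assumed. The observable rate is p × s, and the chance of seeing at least one case in 5 is 1 - (1 - p × s)^5.

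| s | p = 20%: observable rate | Chance of ≥1 in 5 | p = 25%: observable rate | Chance of ≥1 in 5 |
|---|---|---|---|---|
| 100% | 20% | 0.67 | 25% | 0.76 |
| 75% | 15% | 0.56 | 18.75% | 0.65 |
| 50% | 10% | 0.41 | 12.5% | 0.49 |
| 25% | 5% | 0.23 | 6.25% | 0.28 |

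At p = 20% these are rows of the protocol's own table.

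**The case against.** The best case for the plan has four parts.

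- **Exclusion 2 is itself a requirement.** Section 8.0 has a licensed clinician assess every criterion, and 10.6.1 has a licensed team member review health status and eligibility at clinic visits. The Day 0 list is plainly not exhaustive: the urine pregnancy test within 24 hours of BCG appears under screening. A reader might infer that a participant with new nodes would be dosed. The documents do not support that. They show that the check is missing from the schedule, not that it would be skipped. What stands is the need to reconcile the passages.
- **There is a baseline of a kind.** A reader might infer that none exists. But a general examination is done before BCG, 15.2.1 takes the condition at screening as the baseline for adverse events, and exclusion 2 would keep out anyone with signs on the day. What stands is narrower: no Table 5 grade is scheduled before BCG.
- **Clinicians may examine at their discretion.** The trigger includes clinical assessment as well as history, participants can report unsolicited events, and health status is reviewed at each follow-up visit. It would go too far to say that non-tender nodes are missed. They can be, and the plan would not show whether they were.
- **The effect on conclusions is limited.** Lymphadenopathy is one of six safety parameters, the analysis is descriptive in ten people, and the nodes most likely to be overlooked are Grade 1. Triggered palpation is also stated consistently, so it is a design choice, not a slip. This limits the weight of the point. It does not remove the mismatch between a parameter reported by frequency and severity and an assessment made only in selected participants.

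**Conclusion.** The point holds in two parts. First, exclusion 2 presupposes a dosing-day examination that 10.6.1, the Day 0 list in 11.2 and visit 2 of Appendix B do not list; these passages must be reconciled. Second, a named safety parameter has no scheduled Table 5 baseline and no unconditional node assessment after BCG, so unexamined participants cannot be separated from Grade 0 and the reported frequency may be too low.

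The size of any understatement is unknown. At an assumed true rate of 20%, the chance of seeing a case in a group of 5 runs from 0.67 with full ascertainment to 0.23 if a quarter of affected participants are found. The calculation also assumes that participants are independent and that there are no false-positive findings. The schedule finding rests on the text alone and needs none of these assumptions. This should be corrected, but it does not undermine the trial as a whole.

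**What to change.** 1. Reconcile section 10.6.1, the Day 0 list in 11.2 and the visit 2 column of Appendix B with the dosing-day examination that exclusion 2 presupposes. Record the Table 5 grade at that examination as the node baseline.
2. Make the existing lymphadenopathy row unconditional on Days 8, 15, 28, 56 and 84, so that Table 5, including Grade 0, is completed for every participant. Amend 10.6.1 and 11.2 to match.
3. Report, by group and visit, the number examined, the distribution of grades and the change from the baseline grade. Show participants not examined as missing, not as Grade 0.
4. Settle whether a node first found after Day 56 is documented, since 15.2.1 and 15.3 disagree.

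The cost is a few minutes of palpation per visit in ten participants who already attend, with no new visit or test. Some small incidental nodes will be recorded; the baseline grade helps to interpret them.

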11.0 STUDY SCHEDULE

11.1 **Participant Procedures Schedule**

See Appendix B

11.2 **Clinic Visit Schedule**

Screening visit: A single visit between Days -42 and -1 (visit 1)

- Informed Consent
- Review medical history,
- Review concomitant medications,
- Collect vital signs (oral temperature, pulse, blood pressure),
- Collect height and weight (to calculate BMI),
- General examination,
- Collect urine for dipstick for protein < 1 and negative for glucose and chlamydia/gonorrhea test,

- Blood draw (29mls (6 teaspoons (tsp)) for testing HIV, hepatitis B surface antigen, antibody to hepatitis C virus, syphilis and QuantiFERON®-TB Gold Test. Results of these screening tests must be negative,
- Pregnancy tests for females of childbearing potential (must be negative for eligibility).
 - Serum pregnancy test at screening,
 - Urine pregnancy test within 24 hours prior to enrollment and receipt of Tice® BCG and INH.

Day 0 (clinic visit 2)

- Administration of BCG 2×10^6 cfu Tice® BCG: one intradermal injection in the deltoid region,
 - * Following administration of Tice® BCG, intradermal (ID) site reactions will be assessed for at least 30 minutes.
- Blood draw via venipuncture for immunogenicity and mycobacteria assays: 114.5mls (8 tbs),
- Participants will be instructed on how to use the initial and on-going subject memory aids eCRF device and how to measure and record AEs/SAEs prior to discharge from the clinic,
- In addition, subjects will be instructed to keep the ID challenge site covered with a dressing (sterile gauze, etc.) and all dressings that have been used to cover the ID challenge site will be collected in sealable clear plastic bags. These materials will be collected from subjects at follow-up visits and properly disposed of as biohazard waste. Subjects will also be counseled to avoid any direct contact of drainage with an immunosuppressed person.

Day 1 (clinic visit 3), Day 2 (clinic visit 4), and Day 3 (clinic visit 5)

- Assess ID challenge site,
- Day 3 (clinic visit 5) only: skin biopsy,
- Review health status and AEs/SAEs that were recorded on the memory aid eCRF device,
- Blood draws via venipuncture for immunogenicity and mycobacteria assays:
 - Day 1: 6.5mls (1.5 tsp),
 - Day 2: 6.5mls (1.5 tsp),
 - Day 3: 6.5mls (1.5 tsp),
- Subjects will be reminded to record self-assessments on their redcap survey:
 - Oral temperature (optional)
 - Solicited local and systemic reactions recorded Days 1-114,

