18.1 Sample Size and Power for Outcome Measures

The study is designed to demonstrate the safety, tolerability and feasibility of using intradermal BCG as a model for the evaluation of TB drugs. With 5 participants in each arm and a low number of AE/SAEs expected, the study is not powered for direct comparison of the two study groups. Instead, reactogenicity, AEs and SAEs will be presented with descriptive statistics summarizing each group. Interpretation of differences will rely heavily upon clinical judgment. In the rare event that there is a high frequency safety event of at least 25% in one of the groups there will be a 76% chance of observing at least one event and a 37% chance of observing 2 events in the relevant group. All participants are expected to provide safety data.

True event rate (%)	Pr(0/5)	Pr(≥1/5)	Pr(≥2/5)
5	0.77	0.23	0.02

10	0.59	0.41	0.08
15	0.44	0.56	0.16
20	0.33	0.67	0.26
25	0.24	0.76	0.37

It is expected that BCG will be detectable in all skin biopsies provided 4 days after BCG immunization and that the 3 day INH treatment will eliminate detectable BCG in all participants. Therefore, even with only 5 participants per group there will be power to detect a difference in the number of participants with detectable BCG either by qPCR or culture. The plot below shows that a low rate of BCG detection in the treatment arm (<0.05) and a high rate of detection in the control arm (>0.95) there will be >90% power to detect a difference between the groups (Fisher's exact test, two-sided $\alpha=0.05$). Power will be diminished if the actual detection rates are shifted toward 0.5 for either group. It is assumed all participants will contribute data for this objective.

Descriptive statistical analyses will be conducted with the data generated from the Secondary Endpoints. The analyses will generate hypotheses to be tested in future studies.

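### Fever is graded only from a measured oral temperature, but self-recording is optional and no clinic reading is scheduled in the acute period after BCG, so fever may be under-counted and left ungraded

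*Combined protocol and SAP*

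**What the plan says.** Section 15.1 opens with "Safety will be assessed by the frequency and severity of" and lists among the solicited events "Systemic reactions including fever, chills, malaise/fatigue, headache, night sweats" and others. Table 4 in section 15.2.2 grades fever in three bands of oral temperature: 38.0-38.4, 38.5-38.9, and 39 °C or above. Unlike chills, malaise or headache, fever has no grade based on interference with activity.

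On how the temperature is obtained, the plan says different things in different places:

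- Section 10.6.2, participant self-monitoring: "They can optionally record their oral temperature as well".
- Section 11.2, survey reminder for Days 1 to 3: the item reads "Oral temperature (optional" and stands beside solicited local and systemic reactions that carry no such mark.
- Section 11.2, Days 16 to 114: "Participants can record their temperature if taken".
- Appendix B: the row "Oral temperature reporting" runs over Days 1 to 112 and is not marked optional.
- Table 4 note: vital signs at Day 1 are the baseline, and vital signs are defined there to include oral temperature.

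Section 18.1 says that reactogenicity will be summarised descriptively for each group and adds "All participants are expected to provide safety data". No section says how a participant or day without a temperature is to be counted, or gives a denominator for fever.

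**The concern.** Fever is one of the flu-like BCG reactions described in section 5.8.1, and the rate of BCG-related adverse events is a primary endpoint (section 13.1). The plan asks for the frequency and severity of fever but does not require the one measurement that defines and grades it. Section 5.8.1 says these symptoms last 1 to 2 days, so a reading not taken in that time cannot be recovered later. With 5 participants per group, one missed case moves the observed rate by 1/5, or 20 percentage points.

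**Working it through.** **1. Is there another scheduled temperature?** The section 11.2 visit lists were set against Appendix B.

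- Screening: oral temperature is collected.
- Days 1 to 6: there is a clinic visit every day with a review of health status and adverse events, but neither source schedules a temperature. Appendix B marks vitals (pulse and blood pressure) at screening only.
- Day 4 onward: a targeted examination may be done if indicated by history or reactogenicity. It is not routine.
- Section 10.6.1 says that vital signs including temperature will be collected, but alongside the examinations before BCG and at the final visit. A reading around Day 114 cannot show a 1 to 2 day reaction to an injection on Day 0.
- The Day 1 baseline in Table 4 has no matching entry in the Day 1 visit list or in Appendix B.

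So Table 4 presumes clinic vital signs that the schedule omits. In the acute period the only scheduled source is a self-recorded value that the text makes optional.

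**2. The plan's own figure.** Inputs from section 18.1: n = 5 per group, true event rate p = 0.25.

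- Pr(at least 1 of 5) = 1 - (1 - 0.25)^5 = 1 - 0.2373 = 0.763. The plan states 76%.
- Pr(at least 2 of 5) = 0.367. The plan states 37%, and its table heading makes clear that this means at least two.

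Both reproduce. Both assume that every event is seen.

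**3. Effect of incomplete capture.** Let c be the share of febrile participants who have a qualifying reading. The documents give no value for c, so it is varied as an assumption. The apparent rate is p × c, and Pr(at least 1 of 5) = 1 - (1 - 0.25c)^5.

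| c (assumed) | Apparent rate | Pr(≥1 of 5) | Pr(≥2 of 5) |
|---|---|---|---|
| 1.0 | 25% | 76% | 37% |
| 0.8 | 20% | 67% | 26% |
| 0.6 | 15% | 56% | 16% |
| 0.5 | 12.5% | 49% | 12% |
| 0.4 | 10% | 41% | 8% |
| 0.2 | 5% | 23% | 2% |

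**4. Link to fever duration.** Suppose a temperature is taken on any given day with probability q, independently of fever (also an assumption). Then c = q for a 1-day fever and c = 1 - (1 - q)^2 for a 2-day fever.

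- q = 0.5: c is 0.50 to 0.75, and Pr(≥1 of 5) is 49% to 65%.
- q = 0.7: c is 0.70 to 0.91, and Pr(≥1 of 5) is 62% to 72%.
- q = 0.8: c is 0.80 to 0.96, and Pr(≥1 of 5) is 67% to 75%.

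**5. What a zero would mean.** With no fevers among k participants, the two-sided 95% exact upper limit is 1 - 0.025^(1/k). For k = 5 it is 52%. If only 3 of the 5 had readings (assumed), it is 71%. A bare 0/5 would not tell the reader which applies.

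**The case against.** The best defence is that the plan has other ways to notice a fever. Participants attend daily on Days 1 to 6, each visit reviews health status and adverse events, and chills, malaise, headache and night sweats are solicited. Fever is itself in the solicited list, and solicited systemic reactions are to be recorded without any option, so a participant can report feeling feverish. The optional item is the numeric reading. This stands, and it limits the concern: a symptomatic episode may well be noticed. It still cannot be confirmed or graded under Table 4 without a measurement.

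It also stands that the Appendix B row gives a window and a device without saying that entry is mandatory. It is unreconciled with the optional wording, which is less than a flat contradiction.

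A reader might infer more than the documents support:

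- **That the survey is the only temperature source after screening.** The Table 4 note presumes Day 1 vital signs, and section 10.6.1 can be read to include a temperature at the final examination. What the text supports is that no clinic reading is scheduled in the acute period.
- **That a blank counts as no fever over all participants, so the rate is necessarily biased low.** Section 18.1 only expects everyone to provide safety data. The counting rule is missing. The downward bias follows if unmeasured participants are kept as non-cases, but no section says that they will be.
- **That the groups will differ in who measures.** The trial is open-label, but nothing in the documents shows differential recording, and section 18.1 disclaims a powered safety comparison.

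Finally, independence of recording from fever is an unfavourable assumption. If people measure when they feel unwell, c rises and the loss shrinks.

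**Conclusion.** The concern holds as a gap between what is to be reported and what is required to be measured. Fever frequency and grade may be under-counted, because a short fever can pass without the reading that defines it even when every instruction is followed. The size is unknown. The fall from 76% to 49% rests on an assumed capture of one half and a true rate of 25%. The documents state no fever rate, and the 76% was given for a generic event, so these figures illustrate sensitivity and do not estimate the loss. The absence of a rule for missing readings is a separate omission and leaves the meaning of any reported fever rate open. Neither point undermines the design. Both are worth correcting before data are collected, since the readings cannot be obtained afterwards.

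**What to change.** Reconcile sections 10.6.2 and 11.2, Table 4 and Appendix B:

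- Make oral temperature a required entry over an acute window that the sponsor states, and when feverish after that. It can be taken in the existing survey, at the clinic visits already held on Days 1 to 6, or both.
- Either schedule the Day 1 vital signs that Table 4 uses as baseline, or amend the note.
- Beside each group's fever count, report the number of participants and the number of days with readings. Show days without a reading as missing, not as no fever.
- Do not use a denominator limited to those with readings in place of required measurement. If people measure when unwell, it can bias the rate high: with one febrile participant and readings from 3 of 5, it gives 1/3 = 33%, against 1/5 = 20% if the other four were truly afebrile.

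The cost is wording changes, one required field or clinic entry, a small added burden for participants, and possibly supplying a thermometer. No dose or clinical rule changes.
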